The patient will be contacted to fill out WOMAC and WOMET surveys.

Evaluation at 12 months: (Primary outcome time point)

1. The patient will fill out WOMAC and WOMET surveys
2. The patient will undergo gait analysis

Beyond this time point, patients will be followed for an additional year to address the exploratory aims of the study, particularly those having to do with cartilage thinning and radiographic progression of osteoarthritis. We acknowledge that the information gathered from this point forward may be underpowered, but it will serve as preliminary data for future grant applications.

Evaluation at 18 months:

The patient will be contacted to fill out WOMAC and WOMET surveys.

Evaluation at 24 months:

1. The patient will fill out WOMAC and WOMET surveys.
2. The patient will have standing plain radiographs to assess for progression of osteoarthritis
3. The patient will have MRI of the knee and thigh

Subjects will remain blinded with regards to treatment until the conclusion of the study. At 24 months will ask them if they learned of their treatment and if so, how.

The subjects will be compensated \$100 for study-related travel each time they visit the laboratory.

Detailed Description of Study Techniques:

MRI timing – patient experience and control of activity prior to scan:

Subjects will not have performed any strenuous activity for two hours prior to the MRI. Subjects will always undergo MRI testing following gait testing. Thus, all subjects will have similar mechanical conditions prior to their MRI. This will reduce the potential for confounding short-term effects that could influence articular cartilage thickness measurements.

[figure not shown]
MRI Sequences to be used in this study

Table 2: MR Imaging Protocol at 3.0 T

Sequence	Scan Time	OA Marker
2D IW FSE	4 min	Bone Marrow Lesions, synovitis, effusion, menisci, ligaments
3D T _{1p}	8 min	Cartilage GAG
3D-DESS	8 min	Cartilage Thickness, 3D Cartilage T2 Diffusion Map
3D Sodium	25 min	Cartilage GAG

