Power calculations & bioinformatic analysis. We will test the hypothesis that increased complement activation, cartilage metabolism and/or inflammatory biomarkers are associated with accelerated cartilage loss. We will explore use of (i) predefined indexes of markers of cartilage metabolism (Table 3 above) and markers of inflammation (Table 4 above), and (ii) a combined multivariate test. For the predefined indexes of markers, we will standardize each marker to have standard deviation 1, so an average of 8 independent markers would have a variance 1/8, and an average of 6 a variance of 1/6. For the combined multivariate testing for the cartilage metabolism and the inflammatory markers, we will use 8 and 6 degrees of freedom, respectively, in conjunction with a multivariate Hotelling's T-test. Power calculation: So to achieve an effect (difference in mean index score) of .25 standardized units using a two-sample-test at (0.05 two-sided, power 0.8) would require 29 samples in each group for the 8-marker index, and 43 per group for the 6-marker index.

Statistical Analysis

Randomization:

We will explicitly test if randomization achieved balance between the experimental groups on potentially confounding variables such as age, gender, and body weight. However, confounding may still operate even if the differences between the groups are not statistically significant. Therefore, we will conduct two secondary analyses in which imbalances in important potential confounding variables (duration of symptoms, grade of chondromalacia found on arthroscopic evaluation of the joint, radiographic severity of arthritis (Kellgren-Lawrence), and diagnosis of depression) will be addressed. First, we will simply add these covariates to the primary regression model. However, estimating so many more parameters will inherently reduce the statistical power of the test of the intervention effect. Our second approach solves this problem by first calculating a propensity score (the probability of being in the meniscectomy group based on pre-treatment variables) for each patient, and then using the propensity scores as regression weights in the main regression analysis. This is a state of the art approach for estimating treatment effects in the presence of potential confounding.

Aim 1: *To test the clinical benefit of arthroscopic meniscectomy in the setting of a stable degenerative meniscus tear.*

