Timeline and Targeted/Planned Enrollment Table:

Timeline (months)	Time Frame	2	5	6	10	12	14	18	22	24	26	32	35	36	44	46	48	
Organize and train personnel	0-2 mo	xxxxx																
Secure IRB and R&D Comm Approvals	0-2 mo	xxxxx																
Screen and recruit subjects	2-32 mo		xxxxx	xxxx	xxxx	xxxxx	xxxx	xxxx	xxxx	xxxx	xxxx	xxxx	xxxx					
Three month follow up evaluations	5-35 mo			xxxx	xxxx	xxxxx	xxxx	xxxx	xxxx	xxxx	xxxx	xxxx	xxxx					
One year follow up evaluations (primary)	14-44 mo							xxxx										
Perform interim analysis	Approx 22 mo								X									
Data analysis of primary outcomes	44-46 mo																xxx	
Information dissemination	46-48 mo																xxxx	
Two year follow up evaluations (exploratory)	26-end												xxxx	xxxx	xxxx	xxxx	xxx	xxxx
Follow-on grant preparation	46-48 mo																xxxx	
Subject screening goal	117 total	0	12	16	31	39	47	62	78	86	94	117						
Subject recruitment goal	82 total	0	8	11	22	27	33	44	55	60	66	82						
Subject primary aim completion goal	74 total						0	10	20	25	29	44	52	54	74			
Exploratory aim completion											0	15	22	25	44	49	54	

Note: we will assess the success of our recruitment at the end of 10 months and double our rate of surgery (and thus our opportunities for recruitment at the preoperative evaluation) if we find ourselves behind in recruitment efforts.

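### The 80% power stated for the biomarker indexes does not hold within this trial: the 8-marker figure is miscalculated, and the 6-marker figure needs more patients than will be enrolled

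*Combined protocol and SAP*

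**What the plan says.** The paragraph headed Power calculations & bioinformatic analysis states its aim: "We will test the hypothesis that increased complement activation, cartilage metabolism and/or inflammatory biomarkers are associated with accelerated cartilage loss". Each marker is standardised to SD 1 and the markers are averaged into an index, so that "an average of 8 independent markers would have a variance 1/8, and an average of 6 a variance of 1/6". The target is stated as "So to achieve an effect (difference in mean index score) of .25 standardized units", with a two-sample test at two-sided 0.05 and power 0.8. The result is that this "would require 29 samples in each group for the 8-marker index, and 43 per group for the 6-marker index". A multivariate Hotelling test is planned alongside, with no power figure of its own. The paragraph does not say what the two groups are, how cartilage loss is measured, or at which visit.

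Four other places bear on the numbers:

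- Statistical Analysis, Hypothesis 1a: 82 patients enrolled and 74 completing 12 months, after 10% loss.
- General Study Plan: knee MRI before surgery, at 3 months and at 24 months. The second year of follow-up serves the exploratory aims, including cartilage thinning. On the data after 12 months the plan says: "We acknowledge that the information gathered from this point forward may be underpowered".
- MR Image Segmentation: refers to thickness change being detectable at two years.
- Timeline and Targeted/Planned Enrollment Table: the row "Exploratory aim completion" ends at 54 in month 48, where the timeline stops.

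**The concern.** A power statement tells the later reader how much weight a null result can bear. This one says 80%. A reader who takes it at face value would treat the absence of a marker association as the outcome of an adequately sized test. The stated group sizes imply 58 and 86 patients. The second total is larger than the whole trial, and both are larger than the 54 patients the timeline shows at the two-year evaluation. No primary or Aim 2 conclusion depends on this test. What is at stake is how an exploratory biomarker result is read, and what it is used to plan next.

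**Working it through.** **Inputs.** Difference 0.25; index variance 1/8 or 1/6; two-sided 0.05; power 0.8 (power paragraph). Enrolled 82 and 12-month completers 74 (Hypothesis 1a). Month-48 exploratory completers 54 (timeline).

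**Step 1: standardised effect.** d = 0.25 / √(1/k) = 0.25√k. For k = 8, d = 0.707; for k = 6, d = 0.612.

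**Step 2: reproduce the plan's figures.** Normal approximation: n per group = 2(1.960 + 0.842)² / d².
- 8 markers: 2 × 7.849 / 0.5 = 31.4, so 32. The exact t-test gives 32.4, so 33. The stated 29 does not reproduce. Power at 29 per group is 75% (t-test) or 77% (normal). One-sided testing does not explain it (25 to 26 per group). A t-test with 9 markers, or with 75% power, would give 29, but the plan states neither.
- 6 markers: 2 × 7.849 / 0.375 = 41.9, so 42. The t-test gives 42.8, so 43. The stated 43 reproduces.

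**Step 3: compare with the trial.** The 8-marker index needs 64 to 66 patients (the plan's figure implies 2 × 29 = 58). The 6-marker index needs 2 × 43 = 86, against 82 enrolled.

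**Step 4: two-group power at the numbers available** (exact t-test, independent markers).

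| Patients | Split | 8 markers | 6 markers |
|---|---|---|---|
| 54 (month 48) | 27/27 | 72% | 60% |
| 54 | 18/36 | 67% | 55% |
| 54 | 14/40 | 61% | 49% |
| 74 (all completers) | 37/37 | 85% | 74% |
| 82 (all enrolled) | 41/41 | 88% | 78% |

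The 54 is a calendar count. The timeline has 60 recruited by month 24, and 60 × 0.9 = 54. The remaining 22, recruited up to month 32, reach 24 months between months 48 and 56. The plan gives no loss rate for year 2. If a further 10% were lost (assumption), 74 × 0.9 gives about 66, or 33/33: 81% for 8 markers and 69% for 6.

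**Step 5: continuous analysis, conditional.** Assume that the two groups are a median split of thickness change, that index and thickness change are jointly normal, and that the index SD applies within groups. The implied correlation is r = [d / √(1 + d²/4)] / [2√(2/π)].
- 8 markers: (0.707 / 1.061) / 1.596 = 0.418.
- 6 markers: (0.612 / 1.046) / 1.596 = 0.367.

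Fisher-z power at n = 54 is Φ(atanh(r) × √51 − 1.960): 89% and 78%. Simulation (20,000 runs) gives 90% and 79%, against 71% and 59% for the median split of the same data. If the 0.25 contrasts the top third or quarter with the rest, the continuous test has about 86 to 88% and 74 to 77%.

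**The case against.** The strongest reply is that the limitation is disclosed. The plan calls the second-year aims exploratory, says that the data may be underpowered, and presents them as groundwork for later grants. That stands, and it is why the point is minor. But the remark carries no number and sits in another section, while the power paragraph still says 0.8.

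Three stronger readings are tempting and are not supported.

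- A reader might infer that the design cannot reach 80% for either index under any split. That is true of the 54 patients at month 48 but not of the design. The two-year evaluations are listed as running to the end, and the 8-marker index would have about 85% if all 74 completed, or about 81% at 66. Only the 6-marker index falls short at every count.
- A reader might infer that the plan discards information by dividing patients into fast and slow losers. The power paragraph does not define its groups, so no such split is stated. That the 24-month MRI supplies the cartilage measure is likewise an inference from the visit schedule and the segmentation section.
- A reader might infer that a continuous analysis simply restores the lost power. The gain rests on a median split, joint normality and linearity, none of which is in the documents, and it shrinks with measurement error in thickness. Even in the median-split case above, the 6-marker index only just approaches 80%.

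It can also be said that restating power for the indexes leaves the Hotelling test untouched. That is so, but the plan claims no power for that test.

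**Conclusion.** The point holds as a mismatch between the power paragraph and the rest of the plan. The 8-marker figure is an arithmetic discrepancy: 32 to 33 per group are needed, and 29 gives about 75%. The 6-marker figure is correct arithmetic for a trial larger than this one: 86 needed against 82 enrolled, with 78% as the ceiling for the two-group test.

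At the month-48 count, power is about 72% and 60% with an even split; if all 74 complete, about 85% and 74%. These values rest on the plan's effect of 0.25, on its assumption of independent markers, on both groups coming from trial patients, and on every counted patient having usable marker samples. Positive correlation between markers would raise the index variance and lower power further. The 54 applies only if cartilage loss is taken from the 24-month MRI. Severity is low, because the aim is exploratory and the plan partly concedes the limitation.

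**What to change.** 1. In the power paragraph, replace 29 per group by 32 to 33 for the 8-marker index, or state the input that produces 29.
2. State the power of both indexes at 54 patients (about 72% and 60% with equal groups) and at 74 as the upper case (about 85% and 74%), and say that independent markers are assumed. Say plainly that the 6-marker comparison does not reach 80% even with all 82 patients.
3. Say which visit and which measurement define cartilage loss, and what the two groups are.
4. Optional: make regression of continuous 24-month thickness change on each index the main test, and keep any group comparison descriptive. Its price is the assumption of a roughly linear relation, which a plot of the data can check.

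All of this is SAP wording. It needs no extra patients, samples or scans.

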We will test the hypothesis that increased complement activation, levels of inflammatory cytokines and/or levels of cartilage metabolism biomarkers are associated with accelerated cartilage loss. Biomarkers of cartilage metabolism (Table 3 below) as well as inflammatory cytokines (Table 4 below) will be measured as indicated. The rationale for characterizing inflammatory cytokines, including IL-1 α , IL-6 and TNF, is based on the putative role of these cytokines in driving low-grade inflammation that might contribute to the pathogenesis of OA. Studies on human samples and in mouse models have suggested a role for IL-1 α and other cytokines in OA pathogenesis. Further, IL-1 α and other cytokines modulate neural signals arising from painful stimuli and may thereby exacerbate gait dysfunction in OA. The rationale for analyzing complement components is based on data from our laboratory (Wang et al, 2011) demonstrating elevations of complement components in OA synovial fluid and tissue, and on our data demonstrating that C5-deficient mice are protected against OA (Wang et al, 2011). The cartilage degradation product COMP have been shown by [name]

laboratory to be elevated following exercise, and certain markers of cartilage degradation or synthesis are thought to reflect cartilage turnover, disease severity, or disease progression in OA. The metalloproteinases (MMP) 3 and 13 mediate the proteolytic digestion and subsequent breakdown of cartilage in OA. For certain markers, such as certain collagen degradation products, there are findings suggesting that urine provides a more reliable sample source as compared to serum. We will use the sample source previously demonstrated to be most robust for detection of the biomarker. We will use commercially available ELISA/EIAs (Tables below) to measure the levels of select complement components, cytokines, and cartilage metabolism biomarkers in serum and synovial fluid samples.

Description	Biological fluid to be tested	Symbol	Units	Average (Standard deviation)	Kit source
Cartilage oligomeric matrix protein	serum	COMP	U/L	12.62(4.2)	Pacific Biomarkers
Hyaluronic acid	serum	HA	ng/ml	11.4(4.5)	Corgenix
Chondroitin sulfate 846	serum	CS-846	ng/ml		Ibex
Matrix metalloproteinase-3	serum, SF	MMP-3	ng/ml	64(199)	RnD Systems
Matrix metalloproteinase-13	serum, SF	MMP-13	ng/ml	54(18)	RnD
Type II collagen neopeptide	Serum	C2C	ng/ml		Systems
Keratan sulfate	serum	KS-5D4	ng/ml	27(19)	Ibex

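### The 29 samples per group stated for the 8-marker biomarker index should be 33; on the plan's own inputs 29 per group gives about 75% power, not 80%

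*Combined protocol and SAP*

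**What the plan says.** The paragraph headed Power calculations & bioinformatic analysis proposes two predefined indexes. One covers cartilage metabolism (Table 3) and the other inflammation (Table 4). For scaling, "we will standardize each marker to have standard deviation 1", and the markers are taken as independent, "so an average of 8 independent markers would have a variance 1/8, and an average of 6 a variance of 1/6". The target is "an effect (difference in mean index score) of .25 standardized units", with a two-sample test at "0.05 two-sided, power 0.8". The stated result is that this "would require 29 samples in each group for the 8-marker index, and 43 per group for the 6-marker index". The same paragraph also plans a multivariate Hotelling test with 8 degrees of freedom for the cartilage markers and 6 for the inflammatory ones.

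**The concern.** Every input to the calculation is printed beside its result, so the result can be checked directly. The two figures do not fit each other. With the same difference, error rate and power, the required number is nearly proportional to the index variance. Going from 6 markers to 8 should therefore scale it by about 6/8, and 43 × 6/8 = 32.25. The plan has 29.

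What is at stake is a stated sample size and the power attached to it. A reader who relied on it would think that 58 samples (2 × 29) give 80% power for the 8-marker index, when the plan's own assumptions call for 66 (2 × 33). The plan says that data gathered after month 12 are to serve as preliminary data for later grant applications, so the wrong requirement could be carried forward.

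**Working it through.** **Inputs, all from the Power calculations paragraph.** Difference in mean index δ = 0.25; each marker has SD 1; markers independent; two-sided α = 0.05; power 0.80; equal groups.

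**Effect size.** The average of k independent markers with SD 1 has variance 1/k, so the standardized effect is d = 0.25 / √(1/k) = 0.25 × √k.

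- k = 6: d = 0.25 × 2.4495 = 0.6124
- k = 8: d = 0.25 × 2.8284 = 0.7071

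**Formulas.** Normal approximation: n per group = 2 × [(1.960 + 0.842) / d]². The t-test value solves for n using the noncentral t distribution with 2n − 2 degrees of freedom.

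**Step 1: reproduce the 6-marker figure.** The normal approximation gives 41.9, so 42. The t-test gives 42.8, so 43. The stated 43 reproduces by the t-test, which indicates the method used.

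**Step 2: same method, 8 markers.** The t-test gives 32.4, so 33. The normal approximation gives 31.4, so 32. The stated 29 is 4 short by the first and 3 short by the second.

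**Step 3: power at 29 per group, 8 markers.** The t-test gives 75.4%. The normal approximation gives Φ(0.7071 × √(29/2) − 1.960) = Φ(0.733) = 76.8%. At 33 per group the t-test gives 80.8%.

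**Step 4: look for a reading that yields both 29 and 43.**

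| Variant | 8 markers | 6 markers |
|---|---|---|
| Two-sided 0.05, t-test | 33 | 43 |
| Two-sided 0.05, normal | 32 | 42 |
| One-sided 0.05, t-test | 26 | 34 |
| One-sided 0.05, normal | 25 | 33 |
| Stated | 29 | 43 |

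None of these gives both stated figures. The two-sided t-test with 9 markers gives 28.9, so 29. A variance of 1/9 may have been entered by mistake, but that is an inference and the correction does not depend on it.

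**Step 5: power at sample sizes the trial might supply (8 independent markers, t-test, equal split assumed).**

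- 37 per group (the 74 planned completers halved): 85%
- 27 per group (half of the 54 exploratory-aim completions that the timeline shows by month 48): 72%

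**Step 6: sensitivity to correlation.** The documents give no correlation between markers, so the values of r here are assumptions. With average pairwise correlation r, the index variance is (1 + (k − 1)r)/k. For k = 8 and r = 0.1 this is 1.7/8 = 0.2125 in place of 0.125, and the t-test needs 55 per group. At r = 0.05 it needs 44, and at r = 0.2 it needs 77.

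**The case against.** The strongest reply is that this matters little. The plan calls the synovial and complement work exploratory and concedes that data gathered after 12 months may be underpowered. The trial's size comes from the WOMAC calculation (74 completers, 82 enrolled), and no passage plans to analyse 29 per group. If the 74 completers split evenly, power for 8 independent markers would be 85%, above the target. This stands, and it limits the consequence. It does not make 29 correct. Nor is the even split assured: the paragraph does not define its two groups, the hypothesis concerns accelerated cartilage loss and not treatment arm, and 27 per group would give 72%.

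Three stronger readings are tempting, and the documents do not support them.

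- **That the plan counts 8 cartilage markers where only 7 exist.** Seven rows are visible in Table 3, but that table is visibly broken in the text available: one kit-source name is split across two rows. A lost row cannot be excluded, and the power paragraph uses 8 twice, for the variance and for the Hotelling degrees of freedom. This is a question for the authors.
- **That assuming independence is part of the arithmetic error.** The plan states the assumption openly, and no correlation is given from which to call it wrong. Related markers may well be correlated, but the figures in Step 6 are scenarios. The Hotelling test, which uses the markers' covariance, is also planned.
- **That a null index result would come from a test with less than 80% power.** Power will depend on the number of samples obtained in each group, and the plan does not fix that number.

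**Conclusion.** The stated requirement of 29 per group for the 8-marker index is wrong on the plan's own inputs. The t-test needs 33 (normal approximation 32), and 29 gives about 75% power (77% by the normal approximation). The error is 4 per group, or 8 samples in total. The 43 per group for the 6-marker index is correct under the same t-test and should stay.

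The correction rests on the plan's own assumptions of 8 markers, independence and equal groups. Confidence in the arithmetic is high. The practical weight is low, because the analysis is exploratory and does not drive enrolment. The marker count and the effect of correlation remain open queries and are not part of the error.

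**What to change.** Replace 29 with 33 in the Power calculations paragraph and name the test used. Define the two groups being compared, and state the power for the number of samples expected in each.

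As queries, confirm that Table 3 has 8 entries. If it turns out to have 7, the variance and the Hotelling degrees of freedom must follow, and the t-test would need 37 per group. Add a sentence saying that both figures assume zero correlation between markers, ideally with power shown over a small range of assumed correlations.

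The cost is a change of wording and a slightly less favourable stated requirement for an exploratory analysis. No patients are added and the primary analysis is untouched.

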4. The patient will have standing radiographs of the affected knee.

Evaluation at the time of surgery:

At the time of surgery, the patient will be randomized to treatment with either an arthroscopic partial meniscectomy or arthroscopic lavage. Randomization will be done by opening a sealed envelope in the operating room prior to the procedure. To ensure balanced numbers in the two surgical conditions, especially at the time of the interim look, randomization will be done by permuted blocks of size 10, thereby ensuring 5 patients in each group at every increment of 10 enrollees.

Upon initiation of the surgery, a sample of synovial tissue and synovial fluid will be obtained for biochemical analysis. During the operation, the status of the knee joint will be documented. This will include classifying the degree of chondromalacia according to the Outerbridge classification in all three compartments of the knee, and documenting the geometry and pattern of meniscus tear type. Video and photographs will be taken to assist with this documentation and will be stored in a secure manner.

During the operation, the meniscus will be carefully probed. If a large unstable flap of tissue can be displaced into the articulation (such as a bucket handle tear) this torn fragment will be debrided regardless of the result of randomization. This will be done as it is widely believed that it is inappropriate to leave such an unstable tear untreated. Any other tear types that do not result in an unstable flap that can be displaced into the articulation will be either retained or debrided, depending on the result of randomization.

All postoperative contact from this point forward will be made by study personnel who were not involved in the surgery and who do not have knowledge of the randomization result.

At 2 weeks and 6 weeks:

The patient will have regularly scheduled clinic visits at 2 and 6 weeks that are not a part of the study but are just a part of the routine postoperative care of knee arthroscopy patients. Postoperative care as deemed necessary by the treating physician will be provided and could include pain and/or anti-inflammatory medications. Physical therapy is rarely needed. All provided treatments will be recorded in the chart.

Evaluation at 3 months:

1. The patient will fill out WOMET and WOMAC surveys.
2. The patient will undergo gait analysis.
3. The patient will have an MRI of the knee

Evaluation at 6 months:

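### Weighting both arms by the propensity score, as written, neither balances them nor saves power; separately, the valid primary t-test leaves out the baseline WOMAC already collected

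*Combined protocol and SAP*

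**What the plan says.** Statistical Analysis, Randomization, plans two secondary analyses for chance imbalance in four variables: "duration of symptoms, grade of chondromalacia found on arthroscopic evaluation of the joint, radiographic severity of arthritis (Kellgren-Lawrence), and diagnosis of depression".

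- The first is plain adjustment: "First, we will simply add these covariates to the primary regression model". The section warns that the extra parameters will cost power.
- The second is presented as the remedy: "Our second approach solves this problem by first calculating a propensity score". The score is defined as "a propensity score (the probability of being in the meniscectomy group based on pre-treatment variables) for each patient", and the method is completed by "using the propensity scores as regression weights in the main regression analysis". No inverse, no separate weight for the lavage arm and no variance estimator is given.

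On timing, Evaluation at the time of surgery states: "Randomization will be done by opening a sealed envelope in the operating room prior to the procedure". The same section places "classifying the degree of chondromalacia according to the Outerbridge classification in all three compartments of the knee" during the operation and adds: "Video and photographs will be taken to assist with this documentation".

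Aim 1, Hypothesis 1a, makes the primary test a two-sided independent-sample t-test on 12-month WOMAC. Baseline WOMAC is collected before surgery (Preoperative study related evaluation). Its only stated use in the treatment comparison is a sensitivity t-test on change scores. It is not among the four covariates.

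**The concern.** A propensity score balances two groups only when the weights differ by arm, for example its inverse in one arm and the inverse of its complement in the other. Using the score itself in both arms shifts the two covariate distributions together and leaves the gap between them. An analyst who followed the text would report a result as adjusted for imbalance when almost none had been removed.

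The stated motive, protecting power, also looked doubtful. Chondromalacia is graded when the operating team can already know the arm, which affects both secondary analyses.

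The baseline WOMAC point is of a different kind. The t-test is valid, but a covariate already in hand could sharpen both the primary test and the Hypothesis 1b interval for one degree of freedom. The text also refers to a primary regression model, while Hypothesis 1a specifies only a t-test.

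**Working it through.** **The plan's own figure.** Inputs from Hypothesis 1a: 37 per arm, difference 260, SD 392, two-sided alpha 0.05. SE = 392 × √(2/37) = 91.1, so 260/91.1 = 2.85. Power is 81.4% by the normal approximation and 80.4% by the noncentral t. The stated 81% reproduces.

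**Balance, algebra.** Let e(x) be the score and f(x) the overall covariate density. Unweighted, the meniscectomy arm is proportional to e·f and the lavage arm to (1−e)·f. With weight e in both arms they become e²·f and e(1−e)·f. The ratio is e/(1−e) in both cases.

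**Balance, example.** A binary covariate is present in 60% of the meniscectomy arm and 40% of the lavage arm, so e = 0.6 if present and 0.4 if absent.
- Meniscectomy as written: 0.6×0.6 = 0.36 and 0.4×0.4 = 0.16, so 0.36/0.52 = 69%.
- Lavage as written: 0.4×0.6 = 0.24 and 0.6×0.4 = 0.24, so 0.24/0.48 = 50%.
- The gap goes from 20 points to 19. The odds ratio stays at 2.25.
- Inverse weights give 50% in both arms.

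**Balance and power, simulation.** 6,000 runs per setting, 37 per arm, four independent normal covariates, logistic score, true difference 260/392. The documents give no covariate R-squared, so 0, 0.20 and 0.37 are assumptions. Mean absolute standardised difference: 0.185 unweighted, 0.178 as written, 0.018 inverse weights. Monte Carlo error on power is about √(0.8×0.2/6000) = 0.5 points.

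| Analysis | Power, R² 0 | R² 0.20 | R² 0.37 |
|---|---|---|---|
| Unadjusted | 81% | 80% | 82% |
| Weights as written | 79% | 78% | 80% |
| Covariate adjustment | 79% | 86% | 94% |
| Inverse weights, variance allowing for the estimated score | 79% | 86% | 93% |
| Inverse weights, ordinary robust SE | 79% | 80% | 83% |

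The weights as written cost about as much as four useless covariates and do not recover it when the covariates are useful. Correct inverse weights only match covariate adjustment. With the ordinary robust SE they lose that gain: at R-squared 0.37 the mean SE is 0.240 against a true SD of 0.191, and type I error is 1.4%. The variance that allows for the estimated score gives 5.2%.

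**Baseline WOMAC.** The pilot (Preliminary Studies) reports a one-year change of 561 (407 to 714) in 45 patients. SD of change = 153.5/2.015 × √45 = 511, with 95% interval 423 to 645 (chi-square, 44 df). The correlation r between baseline and 12 months is not given. For each assumed r, the 12-month SD s solves s² − 2·r·392·s + 392² = 511². Adjusted power uses residual SD s√(1−r²), 71 df and variance inflated by 71/70.

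| Assumed r | Implied SD | Power, raw v adjusted | 90% half-width for 1b, raw v adjusted (margin 194) |
|---|---|---|---|
| 0.15 | 392 | 80.4% v 80.7% | 152 v 151 |
| 0.3 | 466 | 65.9% v 69.3% | 180 v 173 |
| 0.5 | 578 | 48.0% v 59.1% | 224 v 195 |

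At SD 392, break-even is r = 0.12, and a useless baseline takes 80.4% to 79.8%. With both SDs at 392, the lower limit of 423 for the SD of change gives r = 1 − 423²/(2×392²) = 0.42, and adjusted power of 86.8%.

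**The case against.** Several points on the other side have force.

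- **Shorthand.** Propensity scores as regression weights may be loose wording for inverse weighting. That is possible, but the text does not say so, and even then the standard error must be specified for the promised power to appear.
- **Comparator.** The plan's power claim is against covariate adjustment, not against the t-test. The worry behind it is reasonable: the pilot found no effect of symptom chronicity or psychiatric diagnosis, which are close to two of the four covariates. With useless covariates, a second simulation (8,000 runs) gave the weights as written 78.5% with a robust SE, or 79.8% with a model SE whose type I error was 5.6%, against 77.9% for covariate adjustment. So the possible saving is 0.6 to 1.9 points, only in that case, and never over the plain t-test. At R-squared 0.20 adjustment led, 85.9% against 78.4 to 79.5%.
- **Assumed inputs.** R-squared 0.37 and r 0.5 are not in the documents. At the planned SD and the pilot's implied r of 0.15, baseline adjustment gains only 0.3 points. The pilot also included non-degenerative tears and arthritis grades up to 3, so its SD of change may not carry over. These limits stand, which is why ranges are shown.
- **Regression or t-test.** The two references agree if the primary regression contains arm alone. The plan should say so.
- **Chondromalacia.** It is assessed before resection, and the plan does not say who grades it. Bias is possible, not shown.

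**Conclusion.** The concern holds. As written, the propensity weighting leaves imbalance almost unchanged (0.18 against 0.19 unweighted) and does not solve the power problem it was introduced for. The balance result is exact algebra and needs no assumption beyond the literal text; the power figures rest on assumed covariate R-squared.

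The consequence is limited. These are secondary analyses in a randomised trial, estimates stay unbiased in expectation, and the stated 81% power reproduces. What is at risk is a secondary result labelled as adjusted that is not.

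Leaving out baseline WOMAC is a missed, nearly free improvement. Its value runs from 0.3 points of power (r 0.15, SD 392) to 11 points (r 0.5, SD 578), against a cost of at most 0.6 points. It matters most if the 12-month SD exceeds 392, and then for the Hypothesis 1b interval as well.

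**What to change.** 1. **Propensity analysis.** Drop it and keep the planned covariate adjustment. Otherwise state weights of 1/PS for meniscectomy and 1/(1−PS) for lavage, with a variance that allows for estimating the score (a bootstrap that refits it, or stacked estimating equations).
2. **Covariates.** Use only variables fixed before allocation. Leave chondromalacia out of both secondary analyses, or have it graded from stored images recorded before any resection by a reader who does not know the arm.
3. **Primary model.** Fit a linear model of 12-month WOMAC on arm and baseline WOMAC in each of the ten imputed datasets, and list baseline WOMAC as an imputation variable. Use its adjusted difference and 90% limits for Hypothesis 1b. Keep the raw t-test as a sensitivity analysis, and state which model the interim look uses. This also supplies the primary regression model that the Randomization text refers to. Adding Kellgren-Lawrence grade is optional: if uninformative, it gives 80.2% at r 0.15, no gain over the raw test.

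The cost is SAP wording before unblinding and one degree of freedom, with no new patients or visits. If chondromalacia is kept, add one masked reading of the planned images, provided they include footage from before resection.
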